**Table 4: Measures Needed to Calculate the Deficit Accumulation Frailty Index (DAFI)**

Measure	Item
Demographics	Marital Status
	Telephone
	Travel
	Shopping
	Prepare Meals
	Housework
	Take Medicines
	Handle Money
	Bathing/showering
	Dressing
IADL Instrumental Activities of Daily Living (IADL)	Eating
	Getting out of bed or chairs
	walking
	Using the toilet
Activities of Daily Living (ADL)	Patient Rated KPS
	Number of Falls
	Number of regular medications taken daily
	Other cancer or leukemia
	Arthritis
	Glaucoma
	Emphysema
OARS Comorbidity	High blood pressure

	Heart disease
	Circulation trouble
	Diabetes
	Stomach/Gastrointestinal
	Osteoporosis
	Liver/kidney
	Stroke
	Depression
	Eyesight
	Hearing
Mini Nutritional Assessment (MNA)	Weight loss
Geriatric Depression Scale (GDS)	Depression
Generalized Anxiety Disorder - 7 (GAD7)	Anxiety
	Social activity
Social activities	Change of social activity in the last 6 months
	Comparison of social activity to others their age
	Confined to bed
OARS Medical Social Support	Take to MD
	Prepare Meals
	Daily chores
Physician Rated Karnofsky Performance Status	KPS
Timed-up-and-go (TUG)	Time to complete measure
Montreal Cognitive Assessment (MoCA)	Cognition
Mini Nutritional Assessment (MNA)	Body Mass Index
	Creatinine clearance
Complete Metabolic Panel	Hemoglobin
	Albumin
	Liver Function test

### Assessment of inflammatory markers

We will assess the blood concentrations of several immunological proteins (primary aim) and EGCG (only at the post-intervention time-point (T2)). All blood draws will occur in the Wilmot Cancer Center, UR-affiliated lab, or medical office if needed (in the latter case, we will use a trained study staff member to transport the samples to our storage facility). The location will be selected to minimize subject burden and if possible we will perform blood draws at the same time as regularly scheduled medical blood draw. Patients will report for the blood draw fasted for a minimum of 8 hours on the days of the scheduled blood draws. The blood will be drawn by trained staff and subjects will be informed to bring a breakfast/a snack to eat after the blood draw. The time of day will be noted, with future assessments at approximately the same time of day during post-testing.

A total of approximately 65-70 mL of blood (around 5 tablespoons) will be drawn at each time point (T1 and T2). All tubes will be collected by a study team member, processed, and then transferred to a secured -80°C freezer in lab space maintained by [name] in the Department of Surgery. We will collect the following:

1. Two red-top tubes for serum (10 mL each, 20 mL total). These tubes will be inverted 10 times, allowed to clot for 30 minutes at room temperature, centrifuged for 15 min at 1600 g and then frozen at -20°C or -80°C. These will be used to assess inflammation (cytokines, etc.) and EGCG concentration (only at the post-intervention time-point (T2)).
2. Two purple-top EDTA tubes for biological plasma levels (10 mL each, 20 mL total). One EDTA tube will be rocked 10 times, stored upright for a minimum of 30 min at room temperature and then spun. The other EDTA tube will be rocked 10 times and frozen at -20°C for 2-24 hours and then frozen at -80°C. These will be used to assess genetic biomarkers.
3. Two green-top tubes for peripheral blood mononuclear cells (10 mL each, 20 mL total). These will be pre-cooled and processed per SOP. This tube will be inverted 10 times and allowed to sit at room temp for 30 minutes, centrifuged for 15 min, and then frozen at -20°C or -80°C. These samples will be used to explore transcriptomic and epigenetic differences (using isolated PBMCs) between pre-frail and frail participants (Exploratory Aim 3)
4. Two PAXgene® tubes (2.5 mL each, 5 mL total). These will be used to assess gene expression (i.e., mRNA). These will be rocked 10 times and allowed to sit at room temp for 2-24 hours. Then they will be frozen at -20°C and moved to -80°C for long-term storage.
5. If we need to draw blood for a complete blood count (see below), we will draw one additional purple-top EDTA tube with 5 mL of blood.

If possible, we will obtain a complete blood count from a medical blood draw if the medical blood draw is conducted within the assessment week for T1 or T2. If there is no medical blood draw conducted within the appropriate assessment window for T1 or T2 then we will draw an additional 5 mL of blood (50 mL total) into a purple-

top EDTA tube for a complete blood count with differential analysis for our research purposes.

Inflammation will be assessed using the latest available technology (e.g., in vitro enzyme-linked immunosorbent assay; ELISA). These assays will assess the concentration of inflammatory cytokines and receptors associated with frailty including TNF- $\alpha$ , TNFRI, TNFRII, CRP, IL-1 $\beta$ , and IL-8. Additional blood biomarkers of interest already available in the medical record will be obtained as well. All human biological materials will be disposed of in adherence with the University of Rochester Office of Environmental Safety Biosafety Level II requirements. All laboratories used in the current study have received appropriate biosafety certifications by the University of Rochester Institutional Biosafety Committee and undergo routine inspections. All samples will be de-identified before being stored.

The serum concentration of EGCG at the post-intervention time-point (T2) will be assessed using the latest available technology (e.g. ultra-performance liquid chromatography-tandem mass spectrometry (UPLC-MS/MS)) available by the URMC mass spectrometry resource lab.

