## **5.5 Baseline assessment (T1)**

The following assessments will be completed prior to randomization, preferably within one week of screening assessment (T0). Subjects have the option of completing the screening and baseline assessments on the same day. Due to the ongoing COVID-19 pandemic, some of the baseline measures may be completed either in person, via phone or Zoom.

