#### Other Measures for DAFI calculation

*Physician rated Karnofsky Performance Status (KPS):* The KPS is an index that allows patients with cancer to be classified according to the presence of any functional impairments (e.g. inability to work and care for personal needs). KPS score ranges from 0-100. Low KPS scores are associated with decreased survival in patients with cancer.

*Patient rated KPS:* The patient rated KPS is a patient reported outcome of the presence of any functional impairments.

*Complete Metabolic Panel (CMP):* Study personnel will obtain lab results from the CMP from electronic medical records with dates that are closest to assessment date for baseline assessment (T1) and post-intervention assessment (T2).

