## **5.6 Randomization**

Randomization will be revealed to the subject at the end of the baseline assessment and immediately before delivering the study drug.

We will employ two arms in a 1:1 allocation ratio:

1. EGCG: 12 weeks daily of 800mg EGCG +250mg VitC taken 1 time a day at breakfast (four 200mg EGCG capsules will be packaged with one 250mg VitC tablet)
2. Usual care

Consented subjects will be randomized with a computer-generated random numbers table with block sizes of 2. We will stratify by race (Black vs other) and treatment type (surgery vs other).

The random numbers tables will be generated centrally using software provided by [name], the project biostatistician. A total enrollment of 40 subjects is planned. Due to the study design the PI, study subjects, personnel, and statisticians will be un-blinded to the treatment assignments.

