## **5.8 Study Drug**

Patients will be randomized to one of two treatment arms. Encapsulated EGCG will be supplied by Teavigo. No subject identifiable data will be shared with Teavigo. Each capsule will contain on average 200mg EGCG (94%). Four 200mg EGCG capsules will be packaged with one 250mg VitC tablet and labelled at the pharmacy core at the University of Rochester Medical Center Investigational Drug Service ([name]) into a light resistant pill pouch. At the time of randomization, study personnel will provide subjects with a bag with the 84 pill pouches, the twelve week supply of the study supplement. Instructions on how to correctly take the study drug will be given and reviewed with subjects in Arm 1. Subjects in Arm 1 will be instructed to start taking the study drug on day 1. The study drug will be stored in a secured location within the Cancer Control Unit at URMC that is locked at all times and only accessible by approved study personnel.

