## **5.9 Intervention contact and tracking**

The study coordinator will make every effort to contact each subject 1 time per week via phone calls, and/or emails, (based on each subject's preference) to encourage intervention adherence to the study drug. During this weekly contact the study coordinator will also ask about any safety concerns including: symptoms, signs, illnesses, or experiences, that develop or worsen during the study. These concerns will be graded (according to the CTCAE v5.0 see section 7), recorded, reviewed with the treating oncologist as well as the medical monitor, and reported (if necessary) according to the outline in section 7. If medical information needs to be further discussed, we will set up a phone call, virtual meeting or face-to-face meeting. Study contact will occur from our research staff, which includes study PI, the study staff (coordinators, etc.), and the patient's treatment team (e.g., oncologists, nurses, staff, etc.).

Subjects in the intervention arm will report to URMC labs at weeks four and eight after baseline for a lab draw to determine liver function (ALT, AST, and bilirubin) so that any hepatotoxicity can be monitored. Study personnel will call subjects to remind and coordinate the blood draws.

To track adherence, we will instruct subjects to bring all remaining study drug at their post-intervention assessment (T2) and the pills will be manually counted and pill counts will be entered onto the pill excel document.

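### The T1 chart-lab rules in section 5.5 are not limited to values drawn before randomization, so an EGCG-only week-4 liver result can become the DAFI baseline value

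*Combined protocol and SAP*

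**What the plan says.** Section 5.5 (Baseline assessment) opens with the general rule: "The following assessments will be completed prior to randomization". Two more specific rules follow within the same section.

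- **CMP** (Other Measures for DAFI calculation): results are taken "from electronic medical records with dates that are closest to assessment date for baseline assessment (T1) and post-intervention assessment (T2". No direction, maximum distance or study draw as a fallback is given.
- **Blood count** (Assessment of inflammatory markers): a chart count is used "if the medical blood draw is conducted within the assessment week for T1 or T2". The fallback reads: "If there is no medical blood draw conducted within the appropriate assessment window for T1 or T2 then we will draw an additional 5 mL".

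On the timing of treatment, section 5.6 states: "Randomization will be revealed to the subject at the end of the baseline assessment and immediately before delivering the study drug". Section 5.8 adds: "Subjects in Arm 1 will be instructed to start taking the study drug on day 1". Section 5.9 has EGCG subjects "report to URMC labs at weeks four and eight after baseline for a lab draw to determine liver function". Usual care has no such visits. Section 3.3 accepts a liver test up to three months old at screening, and section 5.2 allows T1 up to four weeks after T0.

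**The concern.** A baseline value should come from before the subject could have been affected by treatment. Nearest in date is not the same as last before. The scheduled source of post-T1 liver results exists in one arm only, so a nearest-date rule can select a pre-treatment value in usual care and an on-treatment value in EGCG. The baseline then means different things in the two arms, and adjusting for it, or subtracting it, removes whatever change had already occurred by that date.

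The outcomes that use these chart labs are the DAFI (Aim 2; Table 4 lists a liver function item) and the circulating cell counts (Aim 3). Section 11.1 says the trial's estimates will inform the design and sample size of the next study.

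**Working it through.** **1. The plan's own figure.** Section 11.1 gives 70% power with 14 per arm, alpha 0.15 (two-sided per 11.2), effect 0.66 and pre-post correlation 0.5. Under ANCOVA the residual SD is √(1 − 0.5²) = 0.866 and the standard error is 0.866 × √(2/14) = 0.327. The ratio is 0.66/0.327 = 2.02. Power is 0.718 by the normal approximation and 0.704 by noncentral t, so the figure reproduces. It concerns FFS, which is measured at T0 and T2 without these labs, so the dating rule does not change it.

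**2. When the week-4 result is nearest to T1.** It falls 28 days after T1. It is selected if the last earlier result is more than 28 days before T1 and nothing else is closer. Assume that:
- the eligibility liver test is the last earlier result;
- its age at screening is uniform over 0 to 90 days;
- the week-4 result is accepted as a CMP liver value.

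| T0 to T1 gap | Lab age at T1 (days) | Share of EGCG subjects taking week 4 as baseline |
|---|---|---|
| 0 days | 0 to 90 | (90 − 28)/90 = 69% |
| 7 days | 7 to 97 | (97 − 28)/90 = 77% |
| 28 days | 28 to 118 | (118 − 28)/90 = 100% |

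The corresponding share in usual care is zero, because no week-4 draw is scheduled there. Any routine chart lab closer to T1 lowers these shares.

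**3. The same rule at T2.** With week 13 taken as day 91, the week-8 draw (day 56) is 35 days away. It is the nearest liver value in EGCG if no chart lab is closer.

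**4. Reach within the DAFI.** Table 4 lists 50 items by count. The safety draws measure ALT, AST and bilirubin, so they can supply only the liver function item. With equal weights that is 1/50 = 0.02 of the index per subject at most.

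**5. Cell counts.** Let p be the share of EGCG subjects whose T1 count is drawn after first dose, and k the share of the final effect present by then. A change score keeps 1 − p·k of the effect, and ANCOVA with slope ρ keeps 1 − ρ·p·k. Neither p nor k is in the documents, and ρ = 0.5 is stated only for FFS. For illustration:

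| p | k | Change score keeps | ANCOVA keeps |
|---|---|---|---|
| 0.10 | 0.25 | 97.5% | 98.8% |
| 0.25 | 0.50 | 87.5% | 93.8% |
| 0.50 | 0.50 | 75% | 87.5% |

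Exposure before such a draw is at most about a week of a 12-week course, so the upper rows are the more plausible ones.

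**The case against.** The strongest reply is that the opening line of 5.5 governs everything under it, so a T1 lab dated after randomization would breach the protocol. That stands in part. The plan does not openly permit such values. But the abstraction rule is explicit and bidirectional, and it conflicts with the opening line when followed literally.

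The blood-count half is weaker, and most of the reply to it stands:
- Neither the assessment week nor day 1 is defined. T1 is in week 0, 84 daily pouches cover 12 weeks, and T2 in week 13 follows completion, so dosing may begin only in week 1.
- The window is about a week, is the same in both arms, and has a study tube as fallback. That tube is triggered only when no medical draw falls in the window, so a narrow gap remains.

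For the liver value, the plan never calls the week-4 draw a CMP. The concern needs that step, and the plan does not exclude it.

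A reader might infer that part of any early EGCG effect is generally removed as baseline, by 25% to 100%. The documents do not support that. Those figures need half or all EGCG subjects to have a post-dose baseline and half or all of the effect to be present by then. No model is written out for cell counts or the DAFI.

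Nor do the documents support the inference that a liver injury would be concealed. The week-4 and week-8 results feed safety monitoring directly (5.9 and section 7), and no baseline-to-T2 liver comparison is specified.

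**Conclusion.** The concern holds in a limited form. The CMP rule is faulty as written: it conflicts with the opening of 5.5 and, combined with draws scheduled in one arm only, can give EGCG subjects an on-treatment baseline liver value. The 69% to 100% shares are conditional on the assumed lab ages, the absence of other labs and the safety draw counting as a CMP result. The consequence is one DAFI item, at most about 0.02 of the index. An effect on Aim 3 cell counts is possible but less likely and would probably be small. FFS, the serum proteins (taken from T1 study tubes), the 70% power and liver safety monitoring are untouched. The gap in the text is certain. The size of any bias is not, and for the main outcomes it is nil. It merits correction because the repair is cheap and a missed pre-dose sample cannot be recovered.

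**What to change.** In section 5.5, for both arms:

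1. Define T1 blood count and CMP values as the last result dated on or before the T1 visit and before randomization, within a stated look-back for each. The present CMP rule has none.
2. If no blood count qualifies, take the extra 5 mL tube already provided for, at the T1 draw.
3. Treat a CMP item with no qualifying value as missing, and say how the DAFI is scored in that case. The complete-case rule in 11.2 could otherwise drop the subject.
4. Bar the EGCG-only week-4 and week-8 draws from serving as T1 or T2 values. Their use for safety is unchanged.
5. Define the assessment week and day 1 relative to T1.

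With this rule no T1 lab can be on treatment, and the dilution above is zero. The cost is a short paragraph, a date check in REDCap, a few more 5 mL tubes and some missing DAFI lab items.

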#### Patient reported outcomes

Quality of Life (QoL): Functional Assessment of Cancer Therapy: Colorectal Cancer (FACT-C): To assess quality of life in patients with colorectal cancer. FACT-C is a 36-item assessment of domains of well-being: physical, social/family, emotional, and functional (specific to Colorectal cancer). Subjects are asked questions related to domains of well-being on a five-point scale (0-4) with 0 being a score of “not at all” and 4 being a score of “very much”. This questionnaire is a well-validated test for assessment of quality of life for patients with cancer receiving treatment. Patients who have colorectal cancer will complete this.

Functional Assessment of Cancer Therapy: General (FACT-G): The FACT-G is a patient-reported outcome measure used to assess health-related quality of life in patients undergoing cancer therapy. Patients with any other cancer except colorectal cancer will complete the FACT-G.

Symptom Burden: MD Anderson Symptom Inventory (MDASI): The MDASI is a 13-item patient reported multi-symptom measure of symptoms found to have the highest frequency and/or severity in patients with cancer. It assesses symptom severity and symptom interference with daily life on a 1-10 scale.

Physical Function: These tests are frequently conducted by our group and are safe with low risk.

*Short Physical Performance Battery (SPPB):* The SPPB is an objective physical assessment evaluating lower extremity physical function. It is comprised of a three-meter walk (subject is asked to do this walk two times and the fastest time is used, so the total distance walked is six meters), repeated chair stands and a balance test. Impairment on SPPB testing has been shown to be predictive of short-term mortality and nursing home admission in community-dwelling older adults.

*Timed-Up-And Go:* The TUG measures, in seconds, the time taken by an individual to stand up from a standard arm chair, walk a distance of three meters, turn, walk back to the chair, and sit down for a total of six meters. The TUG is a measure of functional mobility that correlates to balance and fall risk.

*Yale Physical Activity Survey for Older Adults:* This survey determined the type, amount, and patterning of physical activity/exercise in older adults. It is comprised of two sections. The first section assesses amount of physical activity/exercise performed during a typical week in the past month. The second section assesses the activities performed in the past month.

*GODIN Leisure-Time Exercise Questionnaire:* This short questionnaire is often used to assess leisure-time physical activity in oncology research. It is a 4-item self-administered questionnaire with the first three questions asking about the number of times the patient engages in mild, moderate, and strenuous activities in sessions of at least 15 minutes in a typical week. This questionnaire is used to classify patients as active and insufficiently active according to the North American public health physical activity guidelines.

Epigenetic and proteomic differences

*Data specimen banking for future research.* We will bank blood samples for use in future studies to assess epigenetic and proteomic profiles in pre-frail and frail subjects. We will also keep remaining samples for future research by [name] and her research team. The consent form includes a section asking whether subjects agree to have their samples banked for future studies by [name] and her research team.

## **5.6 Randomization**

Randomization will be revealed to the subject at the end of the baseline assessment and immediately before delivering the study drug.

We will employ two arms in a 1:1 allocation ratio:

1. EGCG: 12 weeks daily of 800mg EGCG +250mg VitC taken 1 time a day at breakfast (four 200mg EGCG capsules will be packaged with one 250mg VitC tablet)
2. Usual care

Consented subjects will be randomized with a computer-generated random numbers table with block sizes of 2. We will stratify by race (Black vs other) and treatment type (surgery vs other).

The random numbers tables will be generated centrally using software provided by [name], the project biostatistician. A total enrollment of 40 subjects is planned. Due to the study design the PI, study subjects, personnel, and statisticians will be un-blinded to the treatment assignments.

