### **1.1 Purpose of the study**

Frailty, an aging-related clinical syndrome associated with low physiologic reserve, is a significant problem for older survivors of cancer. Frailty can be characterized by a combination of symptoms, such as low energy, weakness, slower walking speed, reduced participation in activities, and weight loss to calculate a score based on Fried's frailty criteria. Our group has shown that older survivors of cancer (aged 65+) are at a 46% greater risk of being frail than those without cancer. For older adults with cancer receiving standard of care (surgery with or without chemotherapy), frailty predicts surgical complications, chemotherapy intolerance, and mortality. Unfortunately, no effective treatments for frailty in older survivors of cancer exist. Recently, the National Cancer Institute (NCI) convened a panel of experts for a Think Tank on “Cancer-Related Accelerated Aging” and resolved that trials for frailty in older survivors of cancer are urgently needed.

Inflammation is a major contributor to frailty and a predictor of post-treatment frailty in patients with cancer. Due to the strong association between inflammation and frailty, interventions aimed at reducing inflammation may ultimately reduce frailty and improve post-treatment outcomes for older adults with cancer. Dietary supplements such as epigallocatechin-3-gallate (EGCG) with known anti-inflammatory properties might serve as a practical approach to circumvent chemotherapy-induced frailty in older cancer survivors.

Frailty disproportionately affects African Americans/Blacks (AA/B) who also bear the highest cancer burden. AA/B have a four-fold increased odds of being frail compared to Whites and factors underlying this racial disparity in frailty are unknown. However, research shows that AA/B have elevated inflammatory markers which suggests that inflammation might contribute to the increased risk of frailty. Given the fact that older AA/B with cancer are underrepresented in clinical trials and are at the highest risk of frailty, it is imperative that trials are specifically designed to include this underrepresented group.

This is a two-arm phase 2, single site randomized controlled trial (RCT), oversampling for AA/B, to obtain preliminary data on the feasibility of a 12-week daily EGCG supplementation and on the

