### **4.1 Identification and Recruitment**

We will recruit subjects using our group's established procedures. Before recruitment we will obtain approval by the Institutional Review Board (IRB). We will identify and recruit patients using medical records, advertisements in cancer clinics, and direct referral from nurses and physicians.

***Identification and recruitment via eRecord medical records and MyChart.*** We will identify potential patients who have completed cancer treatment for cancer  $\leq 10$  years prior to screening (i.e.  $\leq 10$  years of completing curative intent treatment).

Study personnel will screen medical records of potentially eligible subjects and confirm with/obtain physician permission to approach the patients. Alternatively, we will let potentially eligible subjects know about the study using MyChart for recruitment at the University of Rochester Medical Center.

Using the study inclusion/exclusion criteria, potential subjects will be identified using information available in eRecord. The study team will review eRecord data on these subjects in order to determine eligibility for this study. Data elements that will be reviewed include: patient's age, cancer diagnosis, last date of cancer treatment, and patient's race.

Potentially eligible subjects will receive an email or text notifying them that they have a new research opportunity available in MyChart. It can only be viewed after they log in to MyChart and visit the Research Studies page. Subjects will see a description of the study, which is included on the attached MyChart for Recruitment Request form (uploaded as part of recruitment materials). Underneath the study description on the Research Studies page, subjects will indicate whether or not they are interested in participating by clicking on the corresponding button. This will trigger a notification that is sent to the study coordinator's InBasket in eRecord.

Interested subjects will then be contacted for screening as described in this protocol. Subjects who are not interested will not be contacted and will be removed from the pool of eligible subjects. If subjects do not indicate whether or not they are interested in participating, they may be re-sent the email notification one additional time, no sooner than one week after the first email was sent.

When study accrual has been completed, outstanding research opportunities in MyChart will be rescinded.

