#### **4.2 Screening**

A study staff member will meet the patient in person or via phone to explain the project, recruit, and screen per inclusion and exclusion criteria in *section 3.3*. We will obtain as much information ahead of time as possible from medical records. If we are meeting with the patient via phone, we

will familiarize the patient with our study and obtain basic eligibility information that was not obtained via medical records.

To ensure we do not approach the same subject twice, we will keep a screening log containing the following information:

- Screening ID (S1, S2, S3, ...)
- Subject name
- Date of contact
- Medical record number
- Gender
- Race/ethnicity
- Where/how we talked to the patient (e.g., phone)
- Whether the patient was eligible or not
- If ineligible, the reason they are ineligible
- Whether the patient consented or declined
- If declined consent, the reason for declining consent
- If consented, the subject ID in the study (C1, C2, C3, ...)

All subjects will need medical clearance from their oncologist (or designee) to participate in the intervention. To familiarize the clinical team with our study procedures we will provide a summary of the study protocol.

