## **5.2 Timing of assessments**

Screening assessment T0 must be completed no more than 10 years after the completion of subject's curative intent cancer treatment. This timing is to ensure that lasting effects of curative intent cancer treatment immune system are minimized and that frailty is still likely to be present. This time frame is also consistent with other survivorship clinical trials.

Assessments T0 and T1 can be completed on the same day. In the event that assessment T0 and T1 are completed on different days, assessment T1 should not occur more than 4 weeks after T0. If for some reason T1 occurs more than 4 weeks after T0, Fried's frailty measures must be repeated to ensure that subjects still meet eligibility criteria. Optimally, assessments T0 and T1 will occur on the same day or within 1 week.

Optimally, assessment T2 will occur during week 13 (within the first week after the completion of study drug), but this may be adjusted (for to no more than 3 weeks after the completion of the study drug) to accommodate factors such as the clinical, subject, and researcher's schedule.

The following table details the approximate study timeline.

Table 1: Approximate study timeline															
Study week		0	1	2	3	4	5	6	7	8	9	10	11	12	13
Study activities	Consent T0	T1*													T2

\*Optimally T1 occurs within 1 week after T0 or on the same day.

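### Fixed blocks of 2 in four strata, run by one un-blinded team, let staff deduce 18 to 20 of the 40 assignments just before randomization, and fewer at approach

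*Combined protocol and SAP*

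**What the plan says.** Section 5.6 Randomization plans 40 subjects allocated 1:1. On the list it states: "Consented subjects will be randomized with a computer-generated random numbers table with block sizes of 2". It names two binary stratification factors, hence four strata: "We will stratify by race (Black vs other) and treatment type (surgery vs other". On blinding, it says that "the PI, study subjects, personnel, and statisticians will be un-blinded to the treatment assignments". The list is generated centrally. The subject learns the assignment at the end of baseline; the section does not say who holds the list or how each assignment is released to staff. Section 1.1 confirms a single site: "This is a two-arm phase 2, single site randomized controlled trial (RCT".

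On what staff know and when:
- Section 4.1, for record review before contact: "Data elements that will be reviewed include: patient's age, cancer diagnosis, last date of cancer treatment, and patient's race". Race is on that list; treatment type is not.
- Section 4.2: "We will obtain as much information ahead of time as possible from medical records".
- Section 4.4 documents surgery and the completed regimen at registration.
- Section 5.2: "Assessments T0 and T1 can be completed on the same day". If they are separated, "assessment T1 should not occur more than 4 weeks after T0". The same paragraph then allows a longer gap if the frailty measures are repeated.
- Sections 5.1 and 5.5 place confirmation of the Fried Frailty Score (FFS) and the baseline assessments before randomization.

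**The concern.** Concealment requires that nobody who influences enrolment can foresee the next assignment. A fixed block of 2 is the easiest block to foresee: once the first subject of a pair is assigned, the next one randomized in that stratum must go to the other arm. One un-blinded team sees every earlier assignment and holds the protocol that states the block size.

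Foreknowledge could affect whether, when or in what order a subject is brought to randomization. Aims 2 and 3 compare EGCG with usual care, and section 11.1 says that the estimates will inform the design and size of the next trial. The Aim 2 model adjusts for baseline FFS and arm only, which would not fully remove selection on unmeasured prognosis. Aim 1 (recruitment, adherence, adverse events) is little affected.

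**Working it through.** The plan gives no figure for predictability, so there is none to reproduce.

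**Inputs.** From the documents: 40 subjects, 1:1, blocks of 2, four strata (5.6); 12 of 40 African American/Black (section 3 enrolment table), so 30%; data acquisition over 18 months and at least 4 patients per month (2.4). I used 40/18 = 2.2 per month and 4 per month. Assumed, because the documents do not give them: a surgery share of 20% or 50%, random arrivals, and a fixed lag from approach to randomization.

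**1. Forced assignments just before randomization.** Forced = sum over strata of floor(n/2) = 20 − (number of odd-sized strata)/2. Four counts that total 40 can include only 0, 2 or 4 odd ones, so forced = 20, 19 or 18. With probabilities of about 1/8, 6/8 and 1/8, the mean is 20/8 + 19×6/8 + 18/8 = 19. The best-guess rate is 0.5 + forced/80 = 0.5 + 19/80 = 73.75%, which is 9.5 correct guesses above chance in 40.

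**2. Known at approach.** A second-of-pair subject counts only if approached after the first of the pair has been randomized. Simulated means, over both surgery shares:

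| Lag | 2.2 per month | 4 per month |
|---|---|---|
| 0 (limiting case) | 19.0 | 19.0 |
| 1 week | 15.4–16.2 | 13.1–14.3 |
| 2 weeks | 12.6–13.9 | 9.3–10.9 |
| 4 weeks | 8.7–10.2 | 5.2–6.4 |

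At 4 per month the figure is about 3 to 4 at 6 weeks and 2 to 2.4 at 8 weeks.

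Hand check with a 50% surgery share: stratum shares are 0.15, 0.15, 0.35 and 0.35, and expected forced counts are (6 − 0.5)/2 = 2.75 (twice) and (14 − 0.5)/2 = 6.75 (twice). The chance that a pair is far enough apart is about exp(−rate × share × lag).
- 2.2 per month, 1 week (0.231 month): 5.5×0.926 + 13.5×0.836 = 16.4, against 16.2 simulated.
- 4 per month, 4 weeks (0.923 month): 5.5×0.575 + 13.5×0.275 = 6.9, against 6.4 simulated. The simulation is lower because long gaps are cut off at the fortieth subject.

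**3. Mixed blocks of 2 and 4.** Here an assignment is certain if it is forced given the history and the possible sizes, so staff are assumed to know the sizes (worst case). Certain assignments average 3.8 to 3.9 of 40. The best-guess rate is about 0.707, or 40×0.207 = 8.3 correct guesses above chance.

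**4. Balance.**
- Blocks of 2: the mean absolute arm difference is 1 with two odd strata and 1.5 with four, so 6/8×1 + 1/8×1.5 = 0.94. P(difference ≥4) = 1/8 × 2/16 = 1.6%. If exactly 12 African American/Black subjects enrol across two strata, P(6/6) = P(both even) + 0.5×P(both odd) = 0.501 + 0.249 = 75%.
- Mixed 2/4 (simulated): mean difference about 1.2, largest seen 6 (against 4), P(difference ≥4) 6–7%, P(6/6) 64–65%, largest within-stratum imbalance 2 instead of 1.

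**The case against.** The strongest reply is that 18 to 20 describes the moment of least discretion. The subject has consented, FFS eligibility is confirmed and baseline is done; steering would mean withholding or re-timing someone already assessed. That stands in large part. What remains open is FFS scoring, medical clearance, and the timing or order of randomization.

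A reader might infer that staff know about 19 of 40 assignments when choosing whom to approach. The documents do not support this. Approach precedes T0; physician permission, clearance and consent (which may be taken home or mailed) lie between; and T1 can fall more than 4 weeks after T0 if the frailty measures are repeated. Doing T0 and T1 on one day therefore does not mean zero lag from approach. Treatment type is not on the pre-approach review list, though it can probably be learned from the record. MyChart notices, advertisements and referral also limit control over who comes forward, and an approached subject may still fail FFS or clearance.

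A reader might also infer that the block size was public during enrolment. Nothing shows that, and it is not needed: staff hold the protocol.

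Central generation, and revealing the assignment to the subject only after baseline, are real safeguards, but neither prevents deduction of a forced second assignment.

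Finally, blocks of 2 protect balance in a 40-subject trial with small strata and a plan for at least 6 African American/Black subjects per arm, and varying the sizes barely lowers the guess rate. Both points are fair. The gain is mainly the removal of certainty, and the balance cost is small but not zero.

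**Conclusion.** The concern holds as an avoidable weakness in concealment: 45% to 50% of assignments (18 to 20 of 40) are deducible just before randomization by staff who track earlier ones. This count follows from the block size, four strata and 40 subjects alone. The approach-stage figures, about 13 to 16 at a 1-week lag and 5 to 10 at 4 weeks, rest on the assumed arrival pattern, lag and surgery share, and are lower at longer lags.

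It would be tempting to conclude that the Aim 2 and Aim 3 estimates are biased. The documents show only an opening; they give no evidence that bias occurs and no basis for calculating its size. In a feasibility trial whose Aim 1 is little affected, this is a change worth making because it is cheap. Confidence is high on the forced count and moderate on its practical impact. The sample size is unaffected.

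**What to change.** In section 5.6:
- Replace the fixed block size of 2 with randomly permuted blocks of randomly varying size within each stratum, for example 2 and 4.
- Keep the sizes out of the protocol and with the biostatistician.
- Release each assignment singly, only after eligibility and the T0 and T1 data are recorded. The order of events is largely in the plan already; single release and undisclosed sizes are new.
- If enrolment has begun, apply this to the remaining assignments.

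The work is a regenerated list and a few edited sentences. The price is the looser balance shown above: mean arm difference from about 0.9 to 1.2 subjects, P(difference ≥4) from about 1.6% to 6–7%, and the chance of a 6/6 split of 12 African American/Black subjects from about 75% to 64–65%.

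The alternatives are less attractive. Fixed blocks of 4 would still leave about 12 certain assignments. Mixed 4/6 would leave about 2 and a 67% guess rate, but would cut the 6/6 chance to about 54–56%. Un-blinded scoring of FFS at T2 is a separate matter that this change does not address.
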